Study design	
A prospective, multicenter, randomized (1:1; DynamX Bioadaptor (ELX1805J): Resolute Onyx), single-blind study, registering approximately 444 subjects at approximately 35 sites within Japan, Europe, and New Zealand to be conducted in two parallel cohorts. The combined Japan Bioadaptor RCT data and European Bioadaptor RCT data are intended to serve as the pivotal trial to support the regulatory approval in Japan with the Pharmaceuticals and Medical Devices Agency (PMDA).
 
Up to 2 de novo lesions located in 2 separate native coronary arteries designated as target lesions may be treated. The target lesion(s) must measure between 2.25 mm and 4.0 mm in diameter and ≤ 34 mm in length, to be covered by a single ELX1805J Bioadaptor or a single control device. Patients should not be randomized until after satisfactory pre-dilatation of the target lesion has been performed.
 
A non-target lesion may be treated if located in separate epicardial vessel (RCA, LCX or LAD) using an approved ‘olimus drug eluting stent provided the treatment of this non-target lesion is done prior to the treatment of the target lesion(s), and the treatment of the non-target lesion is considered successful. The segment should be located such that any injury that might occur during intervention can be clearly attributable to that treated segment.
 
Japanese Cohort (222 subjects) & European/New Zealand Cohort (222 subjects) The study is composed of two cohorts, i.e., the Japanese cohort and the European/New Zealand cohort. For each cohort, at least 222 subjects are randomly allocated in a 1:1 ratio to either the test or control arm. All subjects will receive follow-up clinical assessments at 1, 6 and 12 months and every year for 5 years thereafter. Additionally, imaging follow-up with IVUS and IVUS + OCT are collected in the following imaging subsets. Data from the Bioadaptor RCT European Cohort will be pooled with the data from the Bioadaptor RCT Japan Cohort to support primary and secondary endpoints. The primary endpoint analysis will be performed using the Intent-to-Treat (ITT) population on all subjects at the point of randomization.

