	
IVUS Imaging Subset (80 subjects in the Japanese cohort) The IVUS imaging subset of approximately 80 subjects undergo angiography and IVUS assessments at baseline and 12 month follow-up.
 
IVUS + OCT Imaging Subset (20 subjects in the Japanese cohort) The IVUS + OCT imaging subset of approximately 20 subjects undergo angiography, IVUS + OCT assessments at baseline and 12 month follow-up.
 
Single-group study (referred to as PK substudy) Up to 2 de novo lesions located in 2 separate native coronary arteries designated as target lesions may be treated. The PK study will enroll 8 Japanese subjects and is being conducted to assess the blood pharmacokinetics of Sirolimus eluted from the ELX1805J Bioadaptor implanted in patients. PK measurement will be conducted at pre-treatment, 10 minutes, 30 minutes, 1, 2, 4, 6, 12, 24, 72 hours, and 7 days. In addition, all subjects will undergo clinical follow-up assessments at 1, 6 and 12 months and every year for 5 years thereafter.

Enrollment/ Number of Sites	
Approximately 444 subjects will be enrolled at up to 35 centers in Japan and Europe/New Zealand.
 
Planned: Japanese cohort: 222 European/New Zealand cohort: 222 PK substudy: 8

Study Devices	
Investigational device: ELX1805J (Japan); DynamX Sirolimus Eluting Coronary Bioadaptor System (Europe/NZ)
 
Control device: Resolute Onyx Zotarolimus Eluting Coronary Stent System (Medtronic Japan Co., Ltd. or Medtronic per the applicable geography)
 
PK study: Subjects are to receive the ELX1805J device

Clinical Endpoints:	
Primary Endpoint: Target lesion failure (TLF) assessed at 12 months. TLF is a composite endpoint defined as cardiovascular death, target-vessel MI, and clinically-indicated target lesion revascularization (CI-TLR)
 
Secondary Endpoints: Efficacy endpoints
 
 • Acute success rates: Lesion success rate, device success rate, procedure success rate

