QCA, IVUS, and OCT	
 • Change in vessel angulation from baseline, post-stent and 12-month follow-up • MLD post-procedure and 12 months • % DS post-procedure and 12 months 
IVUS endpoints:
 
 • Change in mean lumen area from post-procedure to 12-month follow-up • In-stent % neointimal obstruction at 12-month follow-up • In-stent late lumen loss at 12-month follow-up • Acute, persistent and late stent malapposition 
OCT Endpoints:
 
 • % Strut coverage • Neointimal thickness • Vessel Pulsatility - % change in Lumen Area and Device Area during systole and diastole by stationary OCT • Additional parameters may be assessed
Key Inclusion Criteria	
Patients who meet all of the following criteria are eligible:
 
 • Patient must be ≥ 20 years of age. • Patient must have evidence of myocardial ischemia (e.g., stable or unstable angina, silent ischemia, positive functional study or electrocardiogram (ECG) changes consistent with ischemia) • Patients who are able to take dual anti-platelet therapy for 1 year following the index procedure and anticoagulants prior to/during the index procedure • The subject is an acceptable candidate for Percutaneous Transluminal Coronary Angioplasty (PTCA), stenting, and emergent Coronary Artery Bypass Graft (CABG) surgery. • The subject or subject's legally authorized representative has been informed of the nature of the study and agrees to its provisions and has provided written informed consent as approved by the Institutional Review Board or Ethics Committee of the respective clinical site. • Women of childbearing potential with a negative pregnancy test within 7 days and women who are not pregnant or nursing • Patient must agree to undergo all clinical study required follow up visits, angiograms, and imaging testing • Patient must agree not to participate in any other clinical research study for a period of one year following the index procedure

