	
Angiographic inclusion criteria- Target Lesion/Vessel
 
Confirmed in QCA assessment:
 
 Target lesion(s) must be de novo and located in a native coronary artery with a vessel mean diameter of ≥ 2.25 and ≤ 4.0 mm assessed 
Confirmed by visual assessment:
 
 Target lesion(s) must be in a major artery or branch with a visually estimated stenosis of $\geq 50\%$ and $< 100\%$ with a TIMI flow of >1. When two target lesions are treated, they must be located in separate major epicardial vessels The visually estimated target lesion length is ≤ 34 mm and must be able to be covered by a single 14/15/18/23/28/32/38 mm ELX1805J stent and have at least 2 mm of healthy vessel on either side, OR The visually estimated target lesion length is ≤ 34 mm and must be able to be covered by a single 15/18/22/30/34/38 mm ZES stent respectively and have at least 2 mm of healthy vessel on either side The lesion(s) must be successfully pre-dilated prior to enrollment Mandatory pre-dilatation includes the use of 2 orthogonal views to confirm lesion inclusion and exclusion criteria. Successful pre-dilatation of a minimum of 1 Target Lesion, defined as no waist in the inflated pre-dilatation balloon (using two orthogonal views) with a pre-dilatation balloon diameter size approximately 0.25 mm smaller than reference vessel diameter but not more than 0.5 mm smaller than the reference vessel diameter. A residual diameter stenosis prior to study device implantation by visual estimate is recommended to be $<30\%$. Percutaneous intervention of lesions in a non-target vessel if: 
 Not part of another clinical investigation ≥ 30 days prior to the study index procedure ≥ 6 months after the study index procedure (planned) Percutaneous intervention of lesions located in the target vessel if: 
 Not part of a clinical investigation ≥ 6 months prior to the study index procedure ≥ 12 months after the study index procedure (planned) Previous intervention was distal to and >10 mm from the target lesion 
Additional inclusion Criteria for PK study Patients participating in PK study may be treated with only ELX1805J

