calculated. Tests are conducted using normal approximation of binomial distribution. When the upper limit of this confidence interval is less than 8.6% (delta of non-inferiority), the null hypothesis is rejected, confirming non-inferiority of investigational device compared to control device for TLF rate at 12 months. This primary analysis will be conducted using the ITT population. Handling of missing data is described in section 3.4.1. In addition, Kaplan-Meier curve for time till first event considered to be TLF will be done. If multiple TLF occurred in same case, occurrence date of the first TLF is the occurrence date of TLF. During study procedure, up to 2 lesions in different epicardial vessels may be treated with the assigned study device. When there are multiple TLF, in a single case, it is counted per case (counted as single incidence).

Analysis of the Secondary Endpoints

Time-dependent response variables can be expressed using Kaplan-Meier curve, and differences in these variables between groups are tested using log-rank test. Data for all categorical endpoints (e.g., TLF rate at a specific time point, etc.) are shown with number of patients, percentage and Clopper-Pearson's exact 95% confidence interval. Differences between treatment groups are shown using 95% confidence interval of the difference. Comparison of imaging corelab endpoints (QCA, IVUS and OCT) in the Japanese cohort will also use the difference between treatment groups and the 95% confidence interval of the difference. Analyses of clinical secondary endpoints are conducted with the PTE population in addition to the ITT population.

Sponsor

Elixir Medical Corporation
 [name]
 [name]
 USA

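### Naming a pre-implant covariate (ANCOVA) for 12-month MLD and change in vessel angulation would narrow two imaging intervals at almost no cost

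*Combined protocol and SAP*

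**What the plan says.** Under Statistical Methods, Analysis of the Secondary Endpoints, the plan states: "Comparison of imaging corelab endpoints (QCA, IVUS and OCT) in the Japanese cohort will also use the difference between treatment groups", together with the 95% confidence interval of that difference. It gives no model and no covariate, there or elsewhere in the available text.

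The QCA list under Imaging Endpoints includes "Change in vessel angulation from baseline, post-stent and 12-month follow-up" and "MLD post-procedure and 12 months".

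Other sections bear on which covariates are available:

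- **Angiographic inclusion criteria (items confirmed by QCA):** "Target lesion(s) must be de novo and located in a native coronary artery with a vessel mean diameter of" 2.25 to 4.0 mm. Vessel diameter is therefore read by QCA to establish eligibility.
- **Study design, timing of randomisation:** "Patients should not be randomized until after satisfactory pre-dilatation of the target lesion has been performed".
- **Study design, imaging subsets:** "The IVUS imaging subset of approximately 80 subjects undergo angiography and IVUS assessments at baseline and 12 month follow-up"; and, for the IVUS + OCT group, "imaging subset of approximately 20 subjects undergo angiography, IVUS + OCT assessments at baseline and 12 month follow-up".
- **Analysis of the Primary Endpoint:** "up to 2 lesions in different epicardial vessels may be treated with the assigned study device". TLF is counted once per subject. No matching rule is given for imaging.

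**The concern.** A raw difference between randomised arms is unbiased, and the plan's wording does not rule out adjustment. The question is whether precision is given up when the trial already holds the data that would recover it.

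Two endpoints stand out:

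- **Change in vessel angulation** is a change score with a genuine pre-implant baseline, since the plan lists baseline separately from post-stent. A raw change score fixes the slope on baseline at 1, whereas ANCOVA estimates it.
- **12-month MLD** is an absolute dimension in vessels that may differ by 1.75 mm in diameter (4.0 − 2.25). Some of its spread between subjects is likely to reflect vessel size, not device performance.

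Both covariates come from pre-procedure images. Randomisation follows pre-dilatation, so the assigned device cannot have influenced them.

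At stake is the width of the intervals that describe how the device behaves at 12 months. The trial's success criterion is not affected.

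**Working it through.** The documents give no SD, power or precision target for any imaging endpoint, so there is no planned figure to reproduce. Results are in SD units.

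**Inputs from the plan:** 80 + 20 = 100 subjects with baseline and 12-month angiography; 1:1 allocation; 95% intervals, taken as two-sided.

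**Assumptions:** an equal split within the subsets (50 per arm), complete data, one lesion per subject, and a correlation r between covariate and outcome of 0.3, 0.5 or 0.7.

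**Formulas**, with N the total number of subjects:

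- Unadjusted half-width: t(0.975, N−2) × √(4/N)
- ANCOVA half-width: t(0.975, N−3) × √(1−r²) × √[(4/N)(1 + 1/(N−4))]
- Change-score SD with equal SDs at both times: √[2(1−r)], multiplied by the unadjusted half-width

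**12-month MLD, N = 100.** Unadjusted: 1.9845 × 0.2 = 0.3969.

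| r | ANCOVA half-width | Narrower by | Equivalent sample size |
|---|---|---|---|
| 0 | 0.3990 | −0.5% (wider) | 0.99 × |
| 0.3 | 0.3806 | 4% | 1.09 × |
| 0.5 | 0.3455 | 13% | 1.32 × |
| 0.7 | 0.2849 | 28% | 1.94 × |

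The last column is the squared ratio of half-widths, for example (0.3969/0.3455)² = 1.32. The two methods break even at r of about 0.103.

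**Change in angulation at 12 months, N = 100.**

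| r (baseline with follow-up) | Raw change score | ANCOVA | Narrower by |
|---|---|---|---|
| 0.3 | 0.4696 | 0.3806 | 19% |
| 0.5 | 0.3969 | 0.3455 | 13% |
| 0.7 | 0.3074 | 0.2849 | 7% |

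Equal SDs are not essential. With baseline SD s0 and follow-up SD s1, the change-score variance minus the ANCOVA variance is (s0² + s1² − 2r·s0·s1) − s1²(1−r²) = (s0 − r·s1)², which is never negative. For example, with s1/s0 = 1.2 and r = 0.7 the variances are 0.760 and 0.734. The only loss is the small-sample 0.5%, reached when r·s1 equals s0.

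Simulation at 50 per arm agreed: about 4%, 13% and 28% for MLD, and 19%, 13% and 7% for angulation.

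**Fewer analysable subjects, N = 80.** The unadjusted half-width is 0.4452, against 0.4275, 0.3881 and 0.3201 adjusted. The MLD percentages move by no more than 0.2 points.

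**OCT, N about 20.** The unadjusted half-width is 0.940. At r = 0.1 ANCOVA gives 0.968, which is wider. Break-even rises to r of about 0.26.

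**Side check on two-lesion subjects.** This matters only if lesions are analysed as independent. Assume 10% to 20% of subjects have two lesions and an intraclass correlation of 0.2 to 0.5.

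- The design effect is 1 + (m−1) × ICC, where m is the size-weighted mean number of lesions per subject: 1.3/1.1 = 1.182 at 10%, and 1.6/1.2 = 1.333 at 20%.
- It runs from 1 + 0.182 × 0.2 = 1.036 to 1 + 0.333 × 0.5 = 1.167.
- Intervals are then too narrow by 1 − 1/√1.036 = 1.8% to 1 − 1/√1.167 = 7.4%, with true coverage of 94.6% down to 93.0%.

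**The case against.** The strongest reply is that nothing is wrong. The raw difference is valid, no imaging endpoint carries a hypothesis, power target or success rule, and choosing between two valid estimators of a descriptive interval is a preference. This is true, and it is why the point is only one to consider. It does not remove the benefit of a narrower interval from data already collected.

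Second, every correlation is assumed. Eligibility limits vessel diameter to 2.25 to 4.0 mm and excludes extreme angulation, which could weaken the correlations; at r = 0.2 the MLD gain is only about 1.5%. This stands as a limit on the size of the gain. Against it, the loss at r = 0 is 0.5%, and for angulation a weaker correlation makes the raw change score worse relative to ANCOVA.

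Third, percent diameter stenosis already expresses narrowing relative to vessel size. That is a separate endpoint, and it does not make the MLD interval any tighter.

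Fourth, the available text is a synopsis, and a fuller statistical section might name covariates. If it does, the point is closed. The one section the synopsis cites, 3.4.1, is cited for missing data.

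Fifth, the angulation endpoint may cover a post-stent contrast as well as a 12-month one, and two-lesion subjects leave the covariate undefined until the unit of analysis is set. Both are fair, and the revised wording needs to deal with them.

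**Conclusion.** The point holds as an inexpensive improvement, not a correction. The plan names no covariate for two QCA endpoints that have a legitimate pre-randomisation one. With about 50 per arm, ANCOVA would narrow the 12-month MLD interval by 4% to 28% for r from 0.3 to 0.7, with no gain below r of about 0.10. It would narrow the angulation-change interval by 19% to 7% over the same range.

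These sizes rest on assumed correlations, an equal split within the imaging subsets, one lesion per subject and, for the angulation percentages, equal SDs. The gain does not carry over to OCT at about 20 subjects, where adjustment can widen the interval. The primary analysis and study success are unaffected.

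**What to change.** In the SAP, prespecify ANCOVA for two endpoints:

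- **Change in vessel angulation:** treatment plus baseline angulation. State which contrast is meant (post-stent, 12 months or both). The N = 100 figures apply to the 12-month contrast.
- **12-month MLD:** treatment plus pre-procedure QCA reference vessel diameter. State whether this is the core laboratory or the eligibility reading, since the documents do not say.

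Allow only pre-implant covariates. Post-procedure MLD follows randomisation and can be affected by the device, so it should not be used. Report the raw difference alongside as descriptive.

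Leave late lumen loss and change in mean lumen area as they are: they are already within-lesion changes, and vessel size may add little. Leave OCT unadjusted, or label any adjusted OCT result as supportive.

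State whether imaging is analysed per subject or per lesion. If per lesion, add a subject random effect or use cluster-robust standard errors.

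The cost is a few lines of SAP text and a standard model. Baseline angiography is already scheduled in both imaging subsets, so no new data are needed. Fixing the model in advance also avoids a choice between raw and adjusted results after the data are seen.
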